Secondary variables:	(1) Total number of postoperative complications per patient; (2) Percent of patients with complications; (3) Total number of stoma related complications per patient; (4) Health-related quality of life; and (5) IPAA functional outcomes (all at 6 months after randomization).
Statistical analysis:	
A Consort Diagram will be used to account for all patients screened for inclusion in the trial; those who were excluded and included and reasons for exclusion; those who were randomized; and those who were followed at each time point or who were lost to follow-up. The primary analysis will be by intention-to-treat, meaning that the patients will be analyzed by the group to which they were randomized. This means that patients randomized to the short interval closure group who have postoperative complications that delay closure will still be analyzed in the group to which they were randomized. Secondary analyses will be done per-protocol (analyzing patients who followed the protocol), and as-treated (analyzing patients by the treatment they actually received).
 
Patient baseline characteristics will be compared between the early and late closure groups using a chi-square test for categorical variables and a t-test for independent samples for normal continuous variables or a Wilcoxon two sample ranks test for non-normal continuous variables.
 
Complications will be reported using the Clavien-Dindo classification. Perioperative details in the two groups will be compared using the same methods as were used for comparing the

Timing of Ileostomy Closure after Ileal Pouch Surgery

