A “defunctioning” loop ileostomy is routine to the practice of colorectal surgery. In general, this type of ileostomy is put in place to direct the enteric contents away from a newly created surgical anastomosis that is downstream (distal) to the ileostomy. For example, a defunctioning loop ileostomy is routinely made during ileal pouch anal anastomosis (IPAA) surgery to facilitate healing of the IPAA. It is common practice to leave the diverting ileostomy in place for 8 to 12 weeks with the idea that this interval is needed to ensure complete healing of the anastomosis. After 8 to 12 weeks, an imaging study (e.g. contrast enema) is performed to confirm complete healing of the anastomosis. After that, so long as healing of the anastomosis has occurred, the diverting ileostomy is surgically reversed. While potentially beneficial to the healing process, a diverting ileostomy may also be detrimental to the health and well-being of the patient. Potential detriments include dehydration, leakage from the ileostomy with resultant skin irritation and interference with activities of daily living, ileostomy dysfunction, and its negative impact on both physical and emotional function and quality of life. In an ideal situation, the diverting ileostomy would be left in place for an adequate period to facilitate healing of the anastomosis, while closing the ileostomy at the earliest appropriate time point in order to minimize the risks associated with an ileostomy.

The primary outcome variable for the study will be the Comprehensive Complication Index (CCI). The CCI is a novel continuous scale to measure surgical morbidity that has been developed in the past few years. (Slankamenac, 2013) It is based upon a survey of patients, nurses, and surgeons measuring their perceptions of the seriousness of 30 postoperative complications common in abdominal surgery (Slankamenac, 2011). From this survey, a score between 0 (no complications) and 100 (death) was developed to measure the occurrence of one or more

Timing of Ileostomy Closure after Ileal Pouch Surgery

postoperative complications in abdominal surgery patients, taking into account the number and seriousness of the complications. The score has been validated using four different methods (K. Slankamenac, 2013), and has been applied to the databases from 3 different randomized surgical trials and shown to be useful in reducing required sample sizes in surgical clinical trials (K. Slankamenac, 2014)

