Quality of life and functional outcomes of IPAA in patients with ulcerative colitis have been evaluated in retrospective studies. (Delaney 2003, Farouk 2000) The SF-12 is a validated quality of life measurement tool that has been used to evaluate patients who have undergone colorectal resection.

JUSTIFICATION AND OBJECTIVES OF THE CLINICAL TRIAL

Randomized prospective trials have evaluated the outcomes of standard (8 weeks) and decreased (8-13 day) intervals to defunctioning ileostomy reversal after rectal cancer surgery and have demonstrated superiority of decreased interval to closure. [Danielsen 2017; Alves 2008] The unique significance of our study is that it will focus on ulcerative colitis patients who undergo ileal pouch surgery with temporary defunctioning ileostomy.

This operation is performed on a minimum of 15 patients, with UC or IC, annually at University of Colorado Hospital and at the co-investigator centers. This surgery is performed by fellowship-trained and board certified colorectal surgeons at the University of Colorado.

Hypothesis: In patients with ulcerative or indeterminate colitis who undergo ileal pouch anal anastomosis and diverting loop ileostomy (IPAA) surgery* a short interval to loop ileostomy reversal will result in differences in complications and quality of life compared to a long interval to loop ileostomy reversal.

*For clarification, please see illustrations and images at end of this document

Aim #1: To compare the Comprehensive Complication Index (CCI), the incidence of postoperative complications, including total number of complications per patient, percent of patients with complications, and total number of ostomy-related complications per patient among IPAA patients who have their ileostomy reversed after a short interval compared to a long interval.

Aim #2: To compare the short vs. long interval groups on measures of health-related quality of life (SF-12) and IPAA functional outcomes

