7. PHASE 2 (day 7 to 12 or week 8-12): Ileostomy Closure:

- a. Early ileostomy closure will be performed at 7 to 12 days after IPAA.
- b. Late ileostomy closure will be performed 8 - 12 weeks after IPAA.
- c. The ileostomy closure surgical technique is at the discretion of the surgeon.
- d. CRF-5 (ileostomy reversal details) will be completed within 3 days of ileostomy reversal surgery.
- e. Endoscopic examination (optional): Rigid and/or flexible endoscopic examination of the IPAA may be performed per standard practice/standard of care, including non-study-related informed consent, at the discretion of the study surgeon following standard of care. (CRF-5)

8. PHASE 2 (day 7 – 12 to 6 months): Outcome assessment:

- a. The Comprehensive Complication Index and postoperative complications will be assessed and recorded by the study surgeon or trial assistant after review of the medical record, conversation with patient, and members of the care team (when appropriate). This assessment and documentation will begin immediately after randomization is performed and will be updated at 1-2 month intervals until 6 months after randomization. (CRF-6)
- b. Functional outcomes and quality of life (CRF-7): IPAA functional outcomes and quality of life (SF-12) will be assessed and recorded once at 6 months after ostomy reversal.

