Case Report Form (CRF)-3 completion (IPAA surgery details)	PHASE 1: Within 2 days of IPAA surgery	REDCap application / surgeon or assistant
Post-IPAA clinical assessment	PHASE 1: Day 5 to 12 after IPAA	Study site inpatient setting / Surgeon
Exclusion of potential study patients judged not clinically suitable for trial entry. Case Report Form (CRF)-4 (IPAA Assessment)	PHASE 1: Day 5 to 12 after IPAA	REDCap application / Study site inpatient setting / Surgeon
Informed Consent #2 - obtained only from potential study patients who are clinically suitable for early ileostomy reversal	PHASE 2: Day 5 to 12 after IPAA, after IPAA clinical assessment	Study site inpatient setting / Surgeon
Radiologic imaging assessment of the IPAA	PHASE 2: Day 5 to 12 days after IPAA	Study site radiology suite
Case Report Form (CRF)-4 completion (IPAA Assessment) - finish	PHASE 2: Day 5 to 12 after IPAA, after IPAA radiological assessment	REDCap application / Study site inpatient setting / Surgeon
Randomization - of study patients who are radiologically suitable for early ileostomy closure	PHASE 2: Day 5 to 12 days after IPAA	Study site trial coordinator office / trial assistant
Ileostomy Closure	PHASE 2: Experimental Arm: 7 to 12 days after IPAA surgery Control Arm: \geq 8 weeks after IPAA surgery	Study site operating room

Timing of Ileostomy Closure after Ileal Pouch Surgery

Case Report Form (CRF)-5 completion (ostomy reversal details)	PHASE 2: Within 2 days of ostomy closure	REDCap application / surgeon or assistant
Outcome Assessment #1- Case Report Form (CRF)-6 (complications)	PHASE 2: 0-1 month after randomization.	REDCap application / surgeon or assistant
Outcome Assessment #2- Case Report Form (CRF)-6 (complications)	PHASE 2: 1-2 months after randomization.	REDCap application / surgeon or assistant
Outcome Assessment #3- Case Report Form (CRF)-6 (complications)	PHASE 2: 2-3 months after randomization.	REDCap application / surgeon or assistant
Outcome Assessment #4- Case Report Form (CRF)-6 (complications)	PHASE 2: 3-4 months after randomization.	REDCap application / surgeon or assistant
Outcome Assessment #5- Case Report Form (CRF)-6 (complications)	PHASE 2: 4-5 months after randomization.	REDCap application / surgeon or assistant
Outcome Assessment #6- Case Report Form (CRF)-6 (complications)	PHASE 2: 5-6 months after randomization.	REDCap application / surgeon or assistant

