Functional outcome and SF-12 Case Report Form (CRF)-7 completion (Function & SF-12)	PHASE 2: At 6 months after randomization	REDCap application / surgeon or assistant
Case Report Form (CRF)-8 completion (Adverse Events)	PHASE 2: Assessed on a daily interval, during hospitalization(s), after IPAA and ostomy reversal surgery and then reassessed at 1-2 month intervals, until 6 months after IPAA.	REDCap application / surgeon or assistant

Clinical Adverse Event Reporting Form

Short versus long interval to loop ileostomy reversal after ileal pouch surgery in patients with ulcerative colitis (SLIRPS) trial

A randomized, prospective trial investigating the timing of diverting ileostomy closure after ileal j-pouch surgery.

Event ID: _____ Study Center: _____ Study ID: _____

Event Name: _____

DOB: ____ / ____ / ____-____ Gender: _____ Race: _____
mm dd yyyy

Name of MD Reporting Event?	_____
Date of Medical Review	____ / ____ / ____-____ mm dd yyyy
Is this a Serious Adverse Event (SAE)?	 Yes  No
Indicate all classifications(s) applicable	 Death  Life threatening  Disability  Congenital anomaly/birth defect  Hospitalization - Initial  Hospitalization - Prolongation  Other
Specify Other	_____
Relationship/Causality (likelihood that study agent caused the event)	 Not related  Probably not related  Possibly related  Related

Timing of Ileostomy Closure after Ileal Pouch Surgery

	Is the event Expected?
	Is the event Unexpected?

Timing of Ileostomy Closure after Ileal Pouch Surgery

MD Narrative:	

Measures at the onset of adverse event
 
 None
 
 Surgical Procedure
 
 Treatment with medication  Other
	
Specify Other:	

Outcome of event (sequelae are defined as conditions following and resulting from event)
 
 Recovered without sequelae
 
 Recovered with sequelae
 
 Not yet recovered
 
 Died
	
Signature of Study Center MD	
Date Form Completed	____ / ____ / ____ - ____ mm dd yyyy

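### The single scheduled SF-12 comes 104 to 139 days, or about 6 months, after a control stoma closed at 8 to 12 weeks, so it measures residual quality of life and not the cost of living with the stoma

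*Combined protocol and SAP*

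**What the plan says.** **Rationale and aim.** Section 2 lists among the possible harms of a diverting ileostomy "its negative impact on both physical and emotional function and quality of life". Under Justification and Objectives, Aim #2 is "To compare the short vs. long interval groups on measures of health-related quality of life (SF-12) and IPAA functional outcomes". The aim names no time point.

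**When SF-12 is taken.** Section 3, item 8b: "IPAA functional outcomes and quality of life (SF-12) will be assessed and recorded once at 6 months after ostomy reversal". The Summary lists quality of life and function among secondary variables that are "all at 6 months after randomization", and the CRF-7 row of the Appendix timeline reads "PHASE 2: At 6 months after randomization". CRF-7 has only that one row. The data lists in Section 4, from screening to outcome assessment, contain no SF-12.

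**When stomas are closed.** Section 3, item 7: "Early ileostomy closure will be performed at 7 to 12 days after IPAA" and "Late ileostomy closure will be performed 8 - 12 weeks after IPAA". Section 3, item 6 and the Appendix timeline set no upper limit for controls; the timeline has "Control Arm: \geq 8 weeks after IPAA surgery".

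**Analysis.** The Summary and Section 10 choose linear mixed models for quality of life on the ground that the scales are recorded repeatedly.

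**The concern.** For patients treated on schedule, the arms differ in stoma status only between early closure and late closure. The quality-of-life harm described in Section 2 acts in that interval, and no SF-12 is taken there. The 6-month assessment asks a different question: whether timing leaves a difference once both arms have been closed for months.

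Suppose the stoma lowers SF-12 and scores recover after closure. The 6-month contrast could then be close to zero although controls had several worse weeks, and a reader could take that as evidence that timing does not matter for quality of life. The missing data cannot be collected once the stomas are closed. The schedule also gives the mixed model one value per patient and no baseline, so there is no within-patient change over time to model.

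**Working it through.** The plan gives no sample-size or power figure for SF-12, so there is none to reproduce on this point. Its CCI figure does reproduce: 2 × (1.96 + 0.84)² × SD² / 10² gives 63 per group for SD 20 and 76 for SD 22. This point does not affect it. The rest is date arithmetic.

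**Inputs** (days after IPAA)
- Randomization R: 5 to 12 (Section 3, item 6).
- Early closure E: 7 to 12 (item 7a), not before randomization.
- Control closure L: 56 to 84 (item 7b, weeks 8 to 12).
- Six months: 6 × 30.44 = 182.6, taken as 183 days.

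**Step 1. Stoma contrast.** L − E runs from 56 − 12 = 44 to 84 − 7 = 77 extra stoma days in controls. SF-12 assessments scheduled in that period: none.

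**Step 2. Randomization clock.** The SF-12 day is R + 183, and time since control closure is R + 183 − L.

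| R | L | SF-12 day | Days since control closure |
|---|---|---|---|
| 5 | 84 | 188 | 104 |
| 12 | 84 | 195 | 111 |
| 5 | 56 | 188 | 132 |
| 12 | 56 | 195 | 139 |

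Early-arm patients closed in window have been closed for 183 − 7 = 176 to 183 days by then.

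**Step 3. Reversal clock.** The SF-12 comes 183 days after closure in both arms: day 190 to 195 for early closure and day 239 to 267 for controls.

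**Step 4. Recall.** The documents give no recall period for the SF-12. Assuming 1 to 4 weeks, the look-back in the closest case (104 days) still starts 104 − 28 = 76 days after closure.

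**Step 5. Open-ended control window.** If closure has no upper limit, a control stoma is still open at 6 months after randomization only when closure falls after day 188 to 195, which is week 26.9 to 27.9. A 28-day recall reaches the stoma period only for closures after (188 − 28)/7 = 22.9 to (195 − 28)/7 = 23.9 weeks. On the reversal clock there is no overlap for any closure date.

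**Step 6. Room for an added assessment** (days after randomization). Early closure falls on day 0 to 12 − 5 = 7. The earliest control closure is 56 − 12 = 44, under either statement of the control window. An SF-12 on day 35 to 43 is therefore at least 35 − 7 = 28 days after in-window early closure and at least 1 day before any in-window control closure. It lies inside Outcome Assessment #2 (1 to 2 months). Day 30 would be too soon: a 28-day recall reaches back to day 2, inside the period when early closures take place.

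**The case against.** **The plan may simply want a medium-term endpoint.** Aim #2 names no stoma-period comparison, the Summary prespecifies 6 months, and this matches the horizon of the primary CCI. CRF-7 pairs SF-12 with pouch function, which cannot be compared before both arms are closed. This stands as far as it goes: the 6-month SF-12 is a legitimate endpoint and should stay. It does not address the harm that Section 2 gives as a reason for closing early.

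**Stoma burden is partly captured.** CRF-6 records stoma complications from randomization. Section 5 defines several of them by interference with daily living, and their number per patient is a secondary variable with its own model. This also stands, so a reader should not infer that the rationale goes wholly untested. These are complications recorded by the surgeon or assistant, however, and not patient-reported quality of life. Living with an uncomplicated stoma is not captured.

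**An early SF-12 mixes effects.** At day 35 to 43 the early arm has had a second operation and is adapting to a new pouch, while controls have not. This is correct, and it limits what the early contrast can be called.

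**The consequences are easy to overstate.** A reader might infer that Aim #2 cannot find any quality-of-life difference, or that a null result is built in. The documents do not support either: a lasting difference remains detectable at 6 months, and no data are given on recovery after closure. Quality of life is also the fourth of five secondary variables, and the sample size rests on CCI alone.

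**Conclusion.** The point holds in a limited form. On either clock, for controls closed at 8 to 12 weeks, the schedule measures only a residual difference in SF-12. The cost while the stoma is in place is not measured by SF-12 at all.

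This rests on closure in window in both arms and on an assumed recall of at most 4 weeks. A reader might infer that no patient could still have a stoma at the SF-12. That follows only from the 8-to-12-week window; with the open-ended wording in Section 3, item 6 and the timeline, a much delayed closure could overlap on the randomization clock. The two statements of the control window must be reconciled, as must the two SF-12 clocks and the single assessment with the repeated-measures model.

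The finding concerns a secondary endpoint and leaves the CCI analysis and sample size unchanged. It is worth acting on because the remedy is cheap and the data cannot be obtained later.

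**What to change.** - Keep the 6-month SF-12 and state one clock for it in Section 3 item 8b, the Summary and the Appendix timeline.
- Add one SF-12, without the pouch-function items, at day 35 to 43 after randomization, within the Outcome Assessment #2 period.
- Fit both times in the planned mixed model with arm, time, arm-by-time and hospital. Report the early contrast as the net effect of the early-closure strategy: stoma avoidance together with recovery from closure and early pouch function. Report the 6-month contrast as the residual effect after closure.
- Reconcile the control closure window between Section 3 items 6 and 7 and the Appendix timeline.

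**Cost.** One 12-item questionnaire, one repeat of the SF-12 part of CRF-7 in REDCap and a short amendment. The contact already exists, but its window becomes tighter: Outcome Assessment #2 spans a month, and Section 3 item 8a allows updates at 1-to-2-month intervals, so sites would have to schedule this one deliberately. Expect a slight patient burden, some missing forms, and an early contrast that cannot separate stoma burden from surgical recovery in one arm only. No extra procedure or patients are needed.

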4 DESCRIPTION OF THE CLINICAL TRIAL SEQUENCE

Screening visit

Data to be recorded:

General parameters:

- Initials
- Age
- Gender
- ASA
- BMI
- Hemoglobin (g/dl)

Timing of Ileostomy Closure after Ileal Pouch Surgery

- Serum Albumin (g/dl)
- Active smoker (smoking within 1 month of IPAA)
- Bowel Preparation (choose: none, mechanical only, oral antibiotic only, mechanical AND oral antibiotic) Date of birth

Case history

Medication Use

- Anti TNF drug use within 8 weeks of IPAA surgery date
- Steroid use within 4 weeks of IPAA surgery date (excluding Budesonide)
- Vedolizumab drug use within 8 weeks of IPAA surgery date
- Other colitis drugs (e.g. methotrexate, azathioprine, 5-ASA) within 4 weeks of IPAA surgery date

Examinations

- Vital signs: blood pressure (mm Hg), heart rate (min^{-1}), weight (kg), calculation of BMI
- Physical examination: Routine preoperative examination
- Blood draw: blood hemoglobin, serum albumin, other blood tests at discretion of surgeon

Formal aspects:

Informed consent procedure

Verification of inclusion / exclusion criteria (eligibility check), as far as possible

PHASE 1, IPAA Surgery

IPAA surgery type

- Proctocolectomy with IPAA (2-stage procedure)
- Completion proctectomy with IPAA (3-stage procedure)

Indication for proctocolectomy or colectomy

- Colitis symptoms inadequately controlled by medical therapy or steroid-dependence
- Colorectal epithelial dysplasia

Timing of Ileostomy Closure after Ileal Pouch Surgery

Urgency of colectomy or proctocolectomy

- Urgent (colectomy or proctocolectomy performed on a hospitalized patient)
- Elective (colectomy or proctocolectomy performed on a patient who was not hospitalized on the day before surgery)

IPAA Surgery Details

- Duration of surgery (cut to close, minutes)
- Open removal of colon and rectum
- Laparoscopic proctocolectomy
- Laparoscopic colectomy with open proctectomy
- Hand assisted laparoscopic (HAL) proctocolectomy
- HAL colectomy colectomy with open proctectomy
- Robotic proctocolectomy
- Robotic colectomy with open proctectomy
- Lap, HAL, or Robotic proctocolctomy or colectomy with unplanned conversion to open surgery
- Trans-anal-trans-abdominal IPAA
- Stapled IPAA
- Sutured IPAA
- IPAA anastomotic leak test performed (yes/no)
- IPAA anastomotic leak test result: no leak, small leak, big leak
- Ileal pouch bleeding that required suture placement or other methods to stop bleeding
- IPAA tension (none, minimal, moderate)
- EBL
- Injury to surrounding structures (specify, enterotomy, ureter injury, pelvic hemorrhage, etc.)
- Sepra Film wrap of ileostomy
- Epidural anesthesia

PHASE 1: IPAA Clinical Assessment

- Post-IPAA day that clinical assessment was performed
- Review / confirmation of inclusion exclusion criteria

Timing of Ileostomy Closure after Ileal Pouch Surgery

- Informed consent #2 obtained (only for patients determined to be clinically suitable for early ileostomy reversal)
- Not ready ileostomy reversal (explanation-comment and Clavien Dindo classification if applicable)

PHASE 2: IPAA Radiological Assessment

- Post-IPAA day that radiologic assessment was performed
- CT with rectal contrast (yes or no)
- Contrast enema (yes or no)
- Radiologic exam OK (Yes or No)
- Randomization to early or late ileostomy closure study arms
- Radiologic exam not OK and patient will NOT be randomized to experimental or control trial arms (explanation required)
- Explanation for no randomization
- Radiologic leak (yes or no, if yes, Clavien-Dindo classification if applicable)
- Other reason for no randomization

PHASE 2: Ileostomy Closure

- Duration of surgery (cut to close, minutes)
- Stapled ostomy closure
- Sutured ostomy closure
- Ostomy site skin complete closure
- Ostomy site skin partial closure (e.g. pursestring)
- Ostomy site skin not closed
- Endoscopic examination of IPAA (no, yes, comments)

PHASE 2: Outcome Assessment

- IPAA stenosis requiring more than simple digital dilation
- Small Bowel Obstruction (imaging confirmed)
- Ileus

Timing of Ileostomy Closure after Ileal Pouch Surgery

- Venous Thromboembolism
- Lung or Heart-related complications
- Hemorrhage requiring transfusion
- high output ileostomy
- Peristomal skin irritation
- Peristomal infection
- ileostomy prolapse
- ileostomy stenosis
- ileostomy revision necessary
- ileostomy leakage
- ileostomy dysfunction

Readmission

- Total # of inpatient hospital days
- Total # of hospital admissions

Comprehensive Complication Index: web-based calculation

